4.16.2. Analyses Stratified by Baseline Concomitant Medications

Exploratory time-to-event analyses of the primary CV endpoint will be performed stratified by the following categories of concomitant medications taken by randomized patients at baseline: antihyperlipidemic agents (Yes/No), antihypertensive agents (Yes/No), and antithrombotic agents (Yes/No). The analyses will be performed using the ITT population.

4.17. Safety Analyses

Unless otherwise noted, all listings and all summary analyses will be conducted using all randomized patients (that is, ITT population). The routine safety analyses will include the measurements of treatment emergent adverse events (TEAEs), serious adverse events (SAEs), laboratory analytes, vital signs, and ECGs.

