### 5.3. Dulaglutide (LY2189265)

Dulaglutide, which contains two analogs of the endogenous hormone GLP-1, is administered as a once-weekly subcutaneous injection to improve glycemic control in patients with type 2 diabetes mellitus. Dulaglutide has received regulatory approval in some countries and is under review in other countries.

The biosynthetic dulaglutide molecule, produced using mammalian cell culture, consists of 2 identical disulfide-linked chains, each containing an N-terminal GLP-1 receptor agonist sequence covalently linked to a human IgG4 heavy chain by a small peptide linker. Dulaglutide has been modified to render the molecule more stable against dipeptidylpeptidase-IV (DPP-IV) inactivation, increase the solubility of the peptide, reduce immunogenic potential, and increase the duration of its pharmacological activity. The pharmacokinetic (PK) half-life of dulaglutide is approximately 5 days, with less than 50% accumulation at steady state, supporting once-weekly dosing. The maximum dulaglutide plasma concentration ( $C_{max}$ ) was observed between 24 and 72 hours following subcutaneous administration.

In clinical trials completed to date, dulaglutide has exhibited the expected GLP-1 receptor agonist pharmacological effect on insulin secretion resulting in significant reductions in glycosylated hemoglobin (HbA1c). Dulaglutide administration in patients with type 2 diabetes has been associated with reductions in body weight. No episodes of severe hypoglycemia have been reported in completed studies. The most common adverse events (AEs) reported in patients administered dulaglutide are those related to the gastrointestinal organ class, including nausea and vomiting. Other AEs that have been rarely reported in trials of dulaglutide include pancreatitis and medullary thyroid cancer (MTC); whether or not these are due to exposure to the analog remains unknown. More detailed information about the known benefits and risks of dulaglutide may be found in the Investigator's Brochure (IB).

The purpose of this trial is to determine whether a once-weekly administration of dulaglutide compared to placebo reduces major adverse CV events, when added to the existing antihyperglycemic regimen of patients with type 2 diabetes who are at high risk for CV events. In addition, it will also assess the effect of the compound on other serious outcomes.

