### **8.3.3. Permanent Discontinuation of Study Drug**

It may be necessary for a patient to permanently discontinue study drug. Investigators should contact the CRO prior to permanent study drug discontinuation. The date of study drug discontinuation will be documented.

Patients who permanently discontinue study drug prior to completing the study will remain in the study to be evaluated for efficacy and safety endpoints and monitored for all visits and testing. If a patient is unwilling or unable to return for future study visits, the site should attempt to collect as much visit information as possible, including through telephone contact, contact with the family or the patient's primary physician, or by searching national registers or deaths indices where permissible by law.

If study drug discontinuation is due to an AE, the event is to be followed according to the procedures in Section 10.2 of this protocol and documented.

Patients will be permanently discontinued from study drug in the following circumstances.

- Enrollment in any other clinical trial involving an investigational product or enrollment in any other type of medical research judged not to be scientifically or medically compatible with this study, and the patient refuses to immediately discontinue from the other clinical trial or medical research.

- The patient's attending physician or the CRO physician requests that the patient permanently stops study drug.
- The patient was inadvertently randomized and, in the opinion of the investigator or the CRO physician, continuation of study drug is not advisable due to safety concerns.
- A patient requires chronic renal replacement therapy (that is, chronic dialysis or renal transplantation).
- A patient is diagnosed with acute or chronic pancreatitis (see Section 10.2.2.1 for criteria to diagnosis acute pancreatitis).
- If after randomization, a patient is observed to have an elevated calcitonin value as described in Section 10.2.2.3.3.1.
- If after randomization, a patient is diagnosed with C-cell hyperplasia or medullary thyroid carcinoma (MTC).
- If an investigator, site personnel performing assessments, or patient is unblinded, the patient must be discontinued from the study drug and the CRO must be notified within one business day.

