4.12. Treatment Exposure and Study Duration

Patients may discontinue study treatment but remain in the study.

Treatment exposure will be defined as the total duration of time that the patient is believed to be taking study drug. This time period will be derived by subtracting the randomization date (Visit 3) minus 1 day from the last visit date for patients actively participating in the study at the time of database lock (at the conclusion of REWIND) or the discontinuation date for patients who discontinue study drug. The duration of treatment exposure will be reported in months and will be compared between treatments using nonparametric methods (Wilcoxon rank-sum tests). The duration of treatment exposure will be summarized by treatment group using the ITT population. The duration of exposure will be categorized into the following groups: ≥ 2 weeks, ≥ 3 months (13 weeks), ≥ 6 months (26 weeks), ≥ 1 year (52 weeks), ≥ 2 years, ≥ 3 years, ≥ 4 years and ≥ 5 years, etc. These categories will be summarized by the number and proportion of patients in each category by treatment group.

Keeping with the ITT principle, the study duration for a patient will commence on the date of randomization to the time of last participation in the study. This will be the patient's safety reporting period. At the time of datalock (at the conclusion of REWIND), the time of last participation will be the Final Visit date for patients still actively participating in the study; the

date of discontinuation if the patient discontinued from the study early; or the date of death if the patient dies during the study. The study duration will be reported in months and will be compared between treatments using nonparametric methods (Wilcoxon rank-sum tests). In addition, a categorical breakdown of the study duration will be provided using the same categories as the duration of treatment exposure.

The number and proportion of patients who discontinue study drug will be compared between treatment groups with separate analyses for the reasons for the discontinuation, (for example, AE, protocol, or patient decision). The length of time patients are off study drug will be summarized by treatment group. The analyses for discontinuations will also be performed by visit.

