4.17.1.2. Analysis of Other Prespecified Safety Measures

Each of the following events will be analyzed using the ITT population: acute pancreatitis, serious GI events, any cancer (excluding basal or squamous cell skin cancer) and specific categories of pancreatic cancer, MTC and C-cell hyperplasia, and thyroid carcinomas, serious hepatic events, clinically significant supraventricular arrhythmias and cardiovascular conduction disorders, serious renal events, discontinuation of study drug for any reason, and immune mediated reactions including serious allergic and hypersensitivity reactions (overall and by type: rash, urticaria, bronchospasm, angioedema, systemic anaphylaxis, erythema multiforme, Stevens Johnson syndrome, toxic epidermal necrolysis, and other). The timing of the allergic/hypersensitivity reactions (immediate reaction - occurs within minutes [<60 minutes], acute reaction - occurs from 1 up to 6 hours from study drug administration, >6 hours through 7 days from study drug administration, and >7 days from study drug administration) will also be summarized and compared between treatment groups. Acute pancreatitis will be analyzed based on adjudicated events and on events as reported by investigators. The analyses of medullary thyroid carcinoma, other thyroid carcinomas, and C-cell hyperplasia will be based on adjudicated events. The analyses of clinically significant supraventricular arrhythmias and cardiovascular conduction disorders and immune mediated reactions including serious allergic and hypersensitivity reactions will be based on SAE reports. The analysis of other cancers (excluding basal or squamous cell skin cancer) will be based on events reported by investigators.

The incidence will be summarized using number and proportion by treatment group for each of the prespecified safety events. The overall number and proportion will be reported. The overall number and proportion will be calculated as the total number of patients and proportion of patients reporting the event during the entire study treatment period. In addition, incidence rates per 100 person-years will be calculated for each of the prespecified safety events. Treatment group comparison will be assessed using a Chi-square or Fisher's exact tests.

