4.17.2. Adverse Events

A patient's safety reporting period will commence on the date of randomization to the time of last participation in the study (Section 4.12).

An AE is defined as any untoward medical occurrence in a patient or clinical investigation subject administered a pharmaceutical product and that does not necessarily have a causal relationship with this treatment. An AE can therefore be any unfavorable and unintended sign (including an abnormal laboratory finding), symptom, or disease temporally associated with the use of a medicinal (investigational) product, whether or not related to the medicinal (investigational) product.

Adverse events will be classified according to the Medical Dictionary for Regulatory Activities (MedDRA™). Analysis of AEs will focus primarily on those events that first occur or worsen (increase in frequency or severity) after the first injection of study drug following randomization, (that is, TEAEs); however, all conditions/events reported on the PRE-EXISTING CONDITIONS AND ADVERSE EVENTS page of the case report form (CRF) will be retained in the study database and will be reported in the listings. Study drug overdose will also be reported as a TEAE. Study drug overdose is defined as documented evidence of study drug injection more than once in a 3-day period. Analyses of TEAEs will be based on all randomized patients.

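### SAP 4.17 compares safety events over all follow-up, on or off drug, and has no on-treatment comparison beside it, so rate ratios for harms confined to exposure are diluted

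*SAP*

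**What the plan says.** The default for safety is that "all listings and all summary analyses will be conducted using all randomized patients (that is, ITT population" (SAP 4.17). The time window is equally broad: "A patient's safety reporting period will commence on the date of randomization to the time of last participation in the study" (SAP 4.17.2), which SAP 4.12 ties to the intention-to-treat principle.

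Follow-up does not end with treatment. SAP 4.12 states: "Patients may discontinue study treatment but remain in the study". Protocol 8.3.3 states: "Patients who permanently discontinue study drug prior to completing the study will remain in the study to be evaluated for efficacy and safety endpoints". Average follow-up is put at about 6.5 years (Protocol Synopsis).

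Treatment-emergent events are those that first occur or worsen "after the first injection of study drug following randomization, (that is, TEAEs" (SAP 4.17.2). Neither this definition nor the one in Protocol Section 4 gives an end relative to the last injection.

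For the other events of special interest, SAP 4.17.1.2 counts patients "reporting the event during the entire study treatment period", compares them by chi-square or Fisher's exact test, and adds incidence per 100 person-years. SAP 4.17.1.1 uses the same period for severe hypoglycemia.

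The only on-drug analysis in either document is the as-treated analysis in Protocol 12.2.1, which covers primary endpoint events only. The SAP's per-protocol analyses concern the primary endpoint and stroke subtypes, plus disposition and baseline tables.

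**The concern.** For superiority on efficacy, counting everyone to the end of follow-up is usually the cautious choice, because dilution works against the claim. For a harm that exists only while the drug is present, the same dilution works toward a reassuring result. Acute pancreatitis, serious gastrointestinal events, hypersensitivity, hepatic events and arrhythmias may be of this kind. The half-life supports a short window: Protocol 5.3 says the "half-life of dulaglutide is approximately 5 days", so five half-lives are about 25 days. Yet an event years after the last dose can still count as treatment-emergent.

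Off-drug time is built into the design. Protocol 8.3.2 provides for temporary stops. Protocol 8.3.3 and parts of 10.2.2 list events after which drug is stopped while follow-up continues. Protocol 7.3 itself warns that poor adherence can harm power.

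The SAP revision history says several events of special interest were added to meet a post-marketing commitment to the regulator, so the sensitivity of these comparisons matters beyond routine reporting.

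**Working it through.** The plan states no figure to reproduce. The check is a reading of the safety sections, as above, and an illustration of the size of the dilution.

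**Assumed, because the documents give no value:** off-drug share of follow-up q, the same in both arms; excess risk only on drug; constant background rate; 20 placebo events over all follow-up. The 0.15% annual dropout in Protocol 12.1 is a sample-size assumption and not a drug-discontinuation rate. **From the documents:** 2-sided alpha 0.05 (SAP 4.2).

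**Formulas**
- Ratio over all follow-up: R = (1 − q) × RR + q.
- Events over all follow-up: placebo 20, dulaglutide 20 × R.
- Events on drug: placebo 20 × (1 − q), dulaglutide 20 × (1 − q) × RR.
- Power (Wald test on the log ratio): Φ( ln(ratio) / √(1/E₀ + 1/E₁) − 1.96 ), where E₀ and E₁ are the placebo and dulaglutide events.

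**Results for RR = 2.0**

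| q | R, all follow-up | Events, all follow-up | Power | Events, on drug | Power | Excess, both counts |
|---|---|---|---|---|---|---|
| 10% | 1.9 | 38 vs 20 | 64% | 36 vs 18 | 67% | 18 |
| 20% | 1.8 | 36 vs 20 | 56% | 32 vs 16 | 62% | 16 |
| 30% | 1.7 | 34 vs 20 | 47% | 28 vs 14 | 56% | 14 |

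Example at 30%: ln 1.7 = 0.531 and √(1/20 + 1/34) = 0.282, so z = 1.88 and power = Φ(−0.08) = 47%. On drug, ln 2 = 0.693 and √(1/14 + 1/28) = 0.327, so z = 2.12 and power = Φ(0.16) = 56%.

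A true ratio of 3.0 at 30% off drug appears as 0.7 × 3 + 0.3 = 2.4.

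The excess is 20 × (1 − q) × (RR − 1) in both counts, so no on-drug event is lost. What shrinks is the ratio, the dulaglutide rate per person-year, and the test statistic.

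**Second model, from a discontinuation rate.** With constant annual permanent discontinuation d and T = 6.5 years, the on-drug share is (1 − e^(−dT)) / (dT). Power is for two proportions with 4800 patients per arm (9600 randomized 1:1), a true ratio of 1.5 and a background rate of 0.3% per year. The values of d, the ratio and the background rate are assumed.

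| d per year | On-drug share | True 1.5 appears as | True 2.0 appears as | Power at 1.5: all follow-up vs on drug |
|---|---|---|---|---|
| 2% | 0.94 | 1.47 | 1.94 | 82% vs 84% |
| 6% | 0.83 | 1.41 | 1.83 | 73% vs 79% |
| 10% | 0.74 | 1.37 | 1.74 | 63% vs 74% |

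At d = 6% and a true ratio of 1.5, the difference in the proportion of patients with an event is 0.789 percentage points over all follow-up and 0.791 on drug. The two models agree.

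**The case against.** The strongest reply is that the choice is deliberate and defensible. The SAP invokes the intention-to-treat principle. On-treatment counts can miss a harm when patients stop for early symptoms and the event is recorded later. All-follow-up analysis is right for delayed harms such as cancer. The main test in SAP 4.17.1.2 is on patient proportions, whose absolute difference hardly changes. SAP 4.12 also summarizes time off drug by arm, so a reader can judge the likely dilution. All of this stands, and it is why the main analysis should not be replaced.

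The power loss is also modest. With no off-drug time the first model gives about 72%. At 30% off drug, the fall to 56% is lost exposure, which no analysis recovers; only the further fall to 47% is dilution.

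Two stronger readings are tempting, and the documents do not support them.

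- A reader might infer that SAP 4.17.1.2 (treatment period) contradicts SAP 4.17.2 (to last participation). The protocol uses the term for the whole post-randomization phase: in the Synopsis, in the heading of 7.1.4, and in the Attachment 1 schedule. On that usage the two sections agree. The phrase is undefined in the SAP, which is a matter for clarification.
- A reader might infer that no safety analysis takes account of dosing. SAP 4.17.1.2 compares hypersensitivity reactions by time from drug administration, and SAP 4.17.2.2 compares adverse events leading to permanent discontinuation. Both come near an on-drug view, but neither limits events and person-time to exposure.

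**Conclusion.** The point holds as an omission. No safety comparison in either document restricts both events and person-time to exposure, and treatment-emergent events have no end after the last injection. For harms confined to exposure, ratios and person-year rates are pulled toward no difference: 2.0 becomes 1.9 to 1.7 if 10 to 30% of follow-up is off drug. With 20 placebo events, the power lost to dilution is about 3 to 9 percentage points.

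These sizes rest on an assumed off-drug share, an assumed event count, and excess risk that ends with exposure. If little follow-up is off drug, the effect is small.

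It would go too far to infer that the intention-to-treat safety analysis is wrong or hides events. It is valid, and the absolute excess is essentially preserved. This is a cheap improvement, best prespecified before unblinding so that the window is not chosen after the fact.

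**What to change.** Keep the intention-to-treat comparison as the main safety analysis. In SAP 4.17.1.1, 4.17.1.2 and 4.17.2.1 add a supportive on-treatment comparison, as follows.

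- **Events:** serious adverse events, acute pancreatitis, serious gastrointestinal events, severe hypoglycemia, immune-mediated reactions, serious hepatic events, and supraventricular arrhythmias and conduction disorders.
- **Window:** events and person-time from the first post-randomization injection to 30 days after the last. This is an analysis convention, slightly longer than five half-lives. For an interruption, remove the part beyond 30 days after the preceding injection.
- **Display:** incidence per 100 person-years beside the intention-to-treat result.
- **Excluded:** cancers, C-cell hyperplasia, and discontinuation of study drug, for which such a window is unsuitable or meaningless.
- **Renal events:** some need two consecutive laboratory values (Protocol 10.2.2.8), and visits are about 6 months apart, so a 30-day limit could drop the confirming value. Date the event at the first value and accept later confirmation, or leave these events intention-to-treat only.

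As a clarification, state in SAP 4.17.1.1 and 4.17.1.2 that the study treatment period means the safety reporting period of SAP 4.12.

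The cost is SAP wording and one more set of tables. Stop and restart dates are already documented (Protocol 8.3.2, 8.3.3). The downside is that randomization does not fully protect on-treatment comparisons, because stopping may be informative, so they should be labelled supportive.

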4.17.1. Prespecified Safety Measures (Adverse Events of Special Interest)

Prespecified safety measures include the incidence of:

- acute pancreatitis
- serious GI events
- any cancer (excluding basal or squamous cell skin cancer) and specific categories of
 - pancreatic cancer
 - medullary thyroid carcinoma (MTC) and C-cell hyperplasia
 - thyroid carcinomas
- severe hypoglycemia
- immune mediated reactions including serious allergic and hypersensitivity reactions
- serious hepatic events
- clinically significant supraventricular arrhythmias and cardiovascular conduction disorders
- serious renal events
- discontinuation of study drug for any reason

4.17.1.1. Analysis of Severe Hypoglycemia

Severe hypoglycemic episodes by patient by visit will be listed using all randomized patients.

The incidence of severe hypoglycemic episodes will be summarized using number and proportion by treatment group and by visit. The overall number and proportion will also be reported as will Kaplan-Meier estimates of the proportion of patients having 1 or more events by treatment group. The number and proportion at each visit are calculated as the number of patients and proportion of patients reporting severe hypoglycemic episodes at that visit. The overall number and proportion are calculated as the total number of patients and proportion of patients reporting severe hypoglycemic episodes during the entire study treatment period. Treatment group comparison will be assessed using a Chi-square or Fisher's exact tests or log-rank tests as appropriate.

Severe hypoglycemia rate per year (number of events per subject per year) will be summarized by yearly visit by treatment group. The rate will be analyzed if enough data points are available. The rate of hypoglycemia will be analyzed using a generalized mixed effect model with a negative binomial distribution (see SAS code below).

```
proc glimmix data=data_glm noitprint empirical initglm method=rspl;
```

```
nloptions maxiter=100 tech=NRRIDG;
class subjid trt visit country stratification variables ;
model count= baseline count country stratification variables trt visit trt*visit/dist=nb
link=log offset=log_days s ddfm=kr;
random visit/subject= subjid type=un residual;
run;
```

An unstructured covariance structure will be used to model the within-patient errors. If this analysis fails to converge, the following covariance structures will be tested in this order: compound symmetry, then, autoregressive. The model will include pooled country, treatment, visit, visit-by-treatment interaction, and baseline. Other covariates of interest, including categorical, continuous and time-dependent may be included.

Time to the first severe hypoglycemia event per patient will also be analyzed via a Cox model described in Section 4.3.4. Incidence rates for 100 person-years will also be presented.

4.17.1.2. Analysis of Other Prespecified Safety Measures

Each of the following events will be analyzed using the ITT population: acute pancreatitis, serious GI events, any cancer (excluding basal or squamous cell skin cancer) and specific categories of pancreatic cancer, MTC and C-cell hyperplasia, and thyroid carcinomas, serious hepatic events, clinically significant supraventricular arrhythmias and cardiovascular conduction disorders, serious renal events, discontinuation of study drug for any reason, and immune mediated reactions including serious allergic and hypersensitivity reactions (overall and by type: rash, urticaria, bronchospasm, angioedema, systemic anaphylaxis, erythema multiforme, Stevens Johnson syndrome, toxic epidermal necrolysis, and other). The timing of the allergic/hypersensitivity reactions (immediate reaction - occurs within minutes [<60 minutes], acute reaction - occurs from 1 up to 6 hours from study drug administration, >6 hours through 7 days from study drug administration, and >7 days from study drug administration) will also be summarized and compared between treatment groups. Acute pancreatitis will be analyzed based on adjudicated events and on events as reported by investigators. The analyses of medullary thyroid carcinoma, other thyroid carcinomas, and C-cell hyperplasia will be based on adjudicated events. The analyses of clinically significant supraventricular arrhythmias and cardiovascular conduction disorders and immune mediated reactions including serious allergic and hypersensitivity reactions will be based on SAE reports. The analysis of other cancers (excluding basal or squamous cell skin cancer) will be based on events reported by investigators.

The incidence will be summarized using number and proportion by treatment group for each of the prespecified safety events. The overall number and proportion will be reported. The overall number and proportion will be calculated as the total number of patients and proportion of patients reporting the event during the entire study treatment period. In addition, incidence rates per 100 person-years will be calculated for each of the prespecified safety events. Treatment group comparison will be assessed using a Chi-square or Fisher's exact tests.

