#### **10.2.2.5. Adverse Event of Interest: Immune-Mediated Reactions and Allergic/Hypersensitivity Reactions**

All immune mediated reactions including allergic or hypersensitivity reactions will be reported by the investigator as either AEs or, if any serious criterion is met, as SAEs. Additional data, such as type of reaction and treatment, will be collected prospectively on any AEs or SAEs that the investigator deems as being related to study drug. Study drug should be temporarily discontinued in any individual suspected of having a severe immune-mediated or severe or serious allergic reaction to study drug (Section 8.3.2). Study drug may be restarted when/if it is safe to do so, in the opinion of the investigator.

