#### **12.2.9.3. Analysis for Other Safety Objectives**

Each of the following events will be analyzed using the ITT population: pancreatitis, any cancer (excluding basal or squamous cell skin cancer), medullary thyroid carcinoma (MTC), C-cell hyperplasia, allergic/hypersensitivity reactions and discontinuation of study drug for any reason. The reasons for temporary discontinuation and reasons for permanent discontinuation of study drug will be summarized. Pancreatitis will be analyzed based on adjudicated events and on events as reported by investigators. The analyses of MTC and C-cell hyperplasia will be based on adjudicated events. The analysis of cancers (excluding basal or squamous cell skin cancer) will be based on events reported by investigators. The incidence will be summarized using frequency and percentage by treatment group and by visit. The frequency and percentage at each visit will be calculated as the number of patients and percentage of patients reporting the event at that visit. The overall frequency and percentage will be reported. The overall frequency and percentage will be calculated as the total number of patients and percentage of patients reporting the event during the entire study treatment period. Treatment group comparison will be assessed using a Chi-square or Fisher's exact test.

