**Study Schedule, Protocol H9X-MC-GBDJ (Concluded)**

Abbreviations: ACR = albumin/creatinine ratio; ALT = alanine aminotransferase; BP = blood pressure; CV = cardiovascular; DCCT = Diabetes Control And Complications Trial Research Group; DSST = the digit symbol substitution test; ECG = electrocardiogram; eCRF = electronic case report form; EVa = Extended follow-up Visit a; EVb = Extended follow-up Visit b; FV = final visit; HR = heart rate; IFCC = International Federation of Clinical Chemistry; IIEF = International Index of Erectile Function Questionnaire; IVRS = interactive voice response system; IWRS = interactive web response system; MoCA = Montreal Cognitive Assessment; SBP = systolic blood pressure.

- a At screening (Visit 1), HR and BP should be measured in both arms in the seated position (triplicates). Only HR and BP measurements from the arm with the higher mean SBP will be recorded; this arm should be used to measure HR and BP at all subsequent study visits. Three measurements should be taken at least 1 minute apart using the same arm. Each measurement of BP/HR is to be recorded on the eCRF.
- b The order of conducting the ECG, vital sign measurements, and blood samples for laboratory testing is determined at the investigative site.
- c Solicitation of new CV or microvascular events, hospitalizations, fractures, cholelithiasis, severe hypoglycemia episodes, allergic/hypersensitivity reactions, cancer, pancreatitis, or thyroid events will be collected and recorded for all visits after randomization.
- d A serum pregnancy test is to be performed at Visit 1 in women of childbearing potential (see Section 8.2); however if this test is unavailable a urine pregnancy test should be performed. A local (urine) pregnancy test should be performed approximately every 6 months thereafter in women of childbearing potential only, unless otherwise indicated, at the discretion of the investigator.
- e HbA1c values, reference range, and standardization method used (DCCT or IFCC) will be recorded on the eCRF. Point of care HbA1c assays will not be acceptable.
- f A morning urine sample for measuring urinary albumin and creatinine and for calculation of ACR is preferred; if not available a spot urine sample will be accepted.
- g Pharmacogenetic sample will be collected 1 time only, preferably at the randomization (Visit 3), but may be collected at any later visit.
- h After Visit 3, injection instructions will be reviewed as needed.

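### The SAP takes its immune-mediated and allergic reaction measure from SAE reports only, which fits neither the protocol's collection and analysis of all such reactions nor the SAP's own type and timing tables

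*SAP*

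**What the plan says.** **SAP 4.17.1.2** lists this measure among the adverse events of special interest. It is to be summarized "overall and by type: rash, urticaria, bronchospasm, angioedema, systemic anaphylaxis, erythema multiforme", with three further categories (Stevens Johnson syndrome, toxic epidermal necrolysis, other). The next sentence adds a table: "The timing of the allergic/hypersensitivity reactions" is to be compared between arms in four bands (under 60 minutes, 1 to 6 hours, over 6 hours to 7 days, over 7 days from injection). The source is then fixed: the analysis of "immune mediated reactions including serious allergic and hypersensitivity reactions will be based on SAE reports".

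**Protocol 10.2.2.5** says that all immune-mediated reactions, allergic ones included, "will be reported by the investigator as either AEs or, if any serious criterion is met, as SAEs". Further detail, such as type and treatment, "will be collected prospectively on any AEs or SAEs that the investigator deems as being related to study drug".

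**Protocol Attachment 1, footnote c** covers solicitation: "allergic/hypersensitivity reactions, cancer, pancreatitis, or thyroid events will be collected and recorded for all visits after randomization".

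**Protocol 12.2.9.3** names the events to be analysed in the ITT population, among them "C-cell hyperplasia, allergic/hypersensitivity reactions and discontinuation of study drug for any reason". It sets no seriousness condition on the allergic reactions.

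**The concern.** The trial asks about allergic reactions at every visit and records the non-serious ones. The one prespecified comparison that pools them as a class then uses only those that met a seriousness criterion. Rash and urticaria are usually non-serious, so a type table headed by those terms suggests that its author had all reactions in mind.

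At stake is how informative a special-interest measure is for a protein injected weekly over years. A pooled comparison of all reactions could show a moderate difference that a count of serious cases would miss. The SAP revision history says that immune-mediated reactions were among the items added in Version 3 to meet a post-marketing commitment to the FDA. It gives no reason for an SAE-only source.

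**Working it through.** There is no planned figure to reproduce: the documents state no incidence, serious share or power for these reactions. The main check compares the texts; the arithmetic after it is illustration.

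**Texts side by side**

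| Step | Place | Seriousness limit? |
|---|---|---|
| Reporting | Protocol 10.2.2.5 | None: AE or SAE |
| Solicitation | Protocol Attachment 1, footnote c | None |
| Type and treatment data | Protocol 10.2.2.5 | None, but only for reactions deemed related to study drug |
| Analysis in the protocol | Protocol 12.2.9.3 | None |
| Analysis in the SAP | SAP 4.17.1.2 | SAE reports only |

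The SAP sentence that sets the SAE source also covers supraventricular arrhythmias and conduction disorders. There the source fits, because Protocol 10.2.2.7 has every clinically significant case listed as an SAE. Protocol 10.2.2.5 has no such rule for immune-mediated or allergic reactions.

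**How many patients the planned tables need.** SAP 4.3.3 gives a relative risk only with at least 10 patients having the outcome. On an even split:
- nine types: 9 × 10 = 90 patients, and 90 / 9600 = 0.94% of those randomized;
- four timing bands: 4 × 10 = 40 patients, and 40 / 9600 = 0.42%.

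**How many an SAE source might supply.** Document input: about 9600 patients randomized 1:1, so 4800 per arm. Assumed inputs: placebo risk of any reaction *p*, serious share *s*, and a risk ratio of 1.5 that is the same for serious and non-serious reactions. Expected patients in both arms:
- all reactions: 4800 × *p* × (1 + 1.5) = 12,000 × *p*;
- serious reactions: 12,000 × *p* × *s*.

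Power is for a two-sided 5% comparison of two proportions (normal approximation).

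| *p* | *s* | All reactions | Serious | Serious per type (÷9) | Serious per band (÷4) | Power, all | Power, SAE only |
|---|---|---|---|---|---|---|---|
| 2% | 5% | 240 | 12 | 1.3 | 3 | 88% | 11% |
| 3% | 10% | 360 | 36 | 4.0 | 9 | 97% | 22% |
| 5% | 20% | 600 | 120 | 13.3 | 30 | >99% | 60% |

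With a lower incidence of 1% in both arms, there are 9600 × 0.01 = 96 patients with any reaction. A serious share of 2% to 20% leaves 1.9 to 19.2 patients, or 0.2 to 2.1 per type.

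The SAE-based type table therefore falls below 10 per type in most of this range and reaches it only at the top corner.

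**The case against.** The case for leaving the SAP alone has several parts.

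- **Non-serious reactions are still analysed.** SAP 4.17.2 compares TEAEs between arms by preferred term and SOC and lists every AE. Preferred terms would show rash and urticaria separately. This stands. What is missing is the pooled class and the timing.
- **The measure's name is ambiguous.** The word *including* may limit the allergic part to serious events, as neighbouring items are limited (serious GI, hepatic and renal events). This stands in part. It would explain an SAE source for allergic reactions but not for immune-mediated reactions, which carry no qualifier.
- **The timing table may not be restricted.** Its sentence speaks of allergic reactions without the word serious, and the SAE sentence uses the full name of the measure. This is a fair reading, and the SAP leaves it unsettled.
- **Type data were never planned for all reactions.** Protocol 10.2.2.5 collects them only where the investigator sees a relation to study drug. This stands and limits what a wider table can show.
- **The SAP may depart from the protocol.** Protocol 12.2.1 allows a non-principal change, with its justification in the SAP and/or the clinical study report. The list in 12.2.9.3 also lacks several current special-interest items. So the departure is not in itself an error, but the SAP gives no reason for it, and the misfit with its own tables remains.
- **A wider measure is less specific.** Over an average of about 6.5 years, many rashes unrelated to treatment would enter it, and neither document defines a term list for non-serious immune-mediated events. This is a real cost.

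**Conclusion.** The mismatch holds on the texts alone. As written, the special-interest measure leaves out reactions that the protocol solicits, records and would analyse, and its source is ill-suited to the type breakdown in the same paragraph. The primary endpoint is untouched. The change is worth making because the reports are already collected.

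The documents do not support three stronger readings:
- *The non-serious reactions are discarded.* They are not: they leave this measure but stay in the TEAE tables and listings.
- *The type and timing tables will be almost empty.* No document gives a rate. Sparse tables are likely over much of the assumed range, but with a 5% incidence and a 20% serious share the SAE-based measure would hold about 120 patients.
- *A true excess would be reported as no difference.* The TEAE comparison is a second prespecified look at the same events. The contrast of 97% with 22% power rests wholly on assumed incidence, serious share and risk ratio, and on equal risk ratios for serious and non-serious reactions. The plan claims no power here, so the figures illustrate the loss and refute nothing.

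**What to change.** In SAP 4.17.1.2:

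1. Keep the SAE-based analysis as one row of the measure.
2. Add a row for all solicited or reported allergic/hypersensitivity and immune-mediated reactions, AE and SAE together. The paragraph already uses two sources for acute pancreatitis (adjudicated and investigator-reported), so the layout has a precedent.
3. Run the type and timing tables on every reaction with the additional data, and label them as reactions that the investigator deemed related to study drug. Protocol 10.2.2.5 names type and treatment as examples of those data but not time since injection, so confirm that the form records it.

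If an SAE-only measure is intended, say so, justify the departure from Protocol 12.2.9.3, and state which source feeds the type and timing tables.

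Cost: a short SAP edit, slightly longer tables, a term list for non-serious immune-mediated events agreed before unblinding, and an all-reactions row that is less specific than the SAE row beside it. No new reporting by sites is needed for the added row.
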